groups.²³ Subsequent analyses led by [name] identified key elements across interventions that mediated successful abstinence in the overall sample.³³ At 6 months, abstinence rates improved significantly with increases in psychosocial factors (i.e., changes in self-efficacy); these mediators eliminated the association of NRT use with smoking abstinence, meeting criteria for complete mediation.³³ A more recently funded R01 across 9 clinics in the Northeast tested a culturally tailored cessation intervention for Latinos living with HIV/AIDS (5R01DA018079; PI, [name]; Co-I, [name]) that yielded similar 7-day ppa rates (8-11% at 6 months; 6-7% at 12 months). However, significant reductions in cigarettes consumed per day were reported.³² Latino smokers born outside the US were significantly more likely to be abstinent at 6 months compared to those born in the US, who tended to be daily heavy smokers with a preference for mentholated cigarettes.^{81,82}

3.C.1.c. Efficacy of the PSF clinic-based cessation intervention among PLWH (R21DA023362; PI, [name]). This RCT tested a clinic-based, group intervention (PSF) for PLWH smokers in comparison to standard care (SC).²¹ Both conditions included nicotine replacement therapy (NRT). 147 subjects were recruited over 12 months in 2009-2010. Recruitment goals were met, and 96% completed the study. At 3 months, biochemically confirmed 7-day ppa was 19.2% in PSF vs. 9.7% in SC. **Higher loneliness score was an independent predictor of treatment failure.** Session attendance was a challenge, with mean attendance of 4 of 8 sessions. Abstinence rates were significantly higher among those who completed ≥ 7 sessions (42.9%). Reasons for non-attendance included difficulty traveling to group sessions, feeling sick, conflicts with other appointments, problems at home, forgetting about sessions, and lack of interest. **Many of these challenges would have been mitigated by Internet access to cessation treatment.**

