3.C.1.e. Efficacy of Positively Smoke Free on the Web among PLWH smokers ([name]/[name] MPIs, R21CA163100-01). This recently published¹⁴ NCI-funded pilot RCT tested a static web-based intervention (PSFW) derived from the content of PSF (3.C.1.c.) compared to SC.¹⁴ 138 subjects were accrued over 13 months (100% of target) and 97% completed the study. At 3 months, biochemically confirmed 7-day ppa was 10.1% among PSFW subjects vs. 4.3% of SC. Of the 8 program sessions, mean number completed was 5.5 sessions, and 40% logged into all 8 sessions (compared to 7% who attended all 8 of the in-person group sessions of the PSF program). 18% of those who logged into all 8 sessions and 31% of the women who completed all 8 sessions were abstinent at 3 months. This promising success rate for women highlights the importance of examining subgroup differences in engagement and efficacy as outlined in our exploratory aim. The adherence protocol was critical: all participants received email reminders to return to the website, and over 94% required at least one reminder phone call from study staff who monitored website utilization throughout the study. Over 78% of participants surveyed post-intervention indicated that the PSFW experience was positive in terms of being helpful, meeting expectations, leading to user satisfaction, and being personally relevant; 95.2% indicated that they would recommend PSFW to family or friends who were interested in quitting. In sum, these results demonstrate Internet access (97%), study feasibility (recruited 100% target on-time), adherence (almost half completed all 8 sessions with mean of 5.5 sessions), efficacy (3 month abstinence was 2.3 times higher in PSFW compared to SC), and satisfaction (95% would refer a friend).

3.C.1.f. Loneliness as central challenge for PLWH smokers.²² Post-hoc analyses were performed on a combined sample (N=272) from the two R21 (PSF & PSFW) trials listed above to explore loneliness in PLWH smokers²²: 63% scored above normal range on a validated loneliness scale,⁸³ and 19% met criteria for extreme

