loneliness. Loneliness was associated with lack of a life partner, alcohol use, depression, anxiety, and lower educational level. Those who were abstinent at 3 months had lower loneliness scores at baseline than those still smoking ($P=0.09$). Loneliness decreased significantly over time among those in the live, group therapy condition, but no changes in loneliness were observed among those in the static PSFW intervention. **[[These findings suggest that the static website failed to reach its full potential due to the absence of a social component, and they provide further justification for the enhancements that we propose in this submission.]]**

[figure not shown]

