3.C.4.c. Recruitment Approach. Participants will be referred by primary care providers at the MMC ID Clinic and the MGUH ID Clinic. Approximately 65% of MMC ID Clinic patients are smokers representing a pool of ~1950 smokers; the MGUH ID Clinic serves an estimated 1200 patients/year, representing a pool of ~780 estimated smokers. These are underestimates since over 500 new PLWH patients enter these care systems annually. Recruitment into the trial will begin in the 4th quarter of Year 1 and will continue for 38 months. Across all sites, we aim to enroll 14.5 subjects/month (7-8/month MGUH; 6-7/month MMC [the lower recruitment target at MMC is in consideration of a concurrent RCT at that site]). Study staff will be on-site full-time at each location throughout the project to enroll participants who are referred by their primary care providers. In our previous PSFW R21 study (3.C.1.e.), conducted at a single site, we recruited N=138 smokers over 13 months (10.6 per month) using the same primary care provider referral strategy. Thus, our target of N=550 over 38 months (14.5/month) should be attainable. In the event we do not meet accrual goals, research staff will directly recruit patients in clinic waiting areas.

3.C.4.d. Study Enrollment and Randomization. Following referral from primary care providers, research staff will conduct eligibility screening and informed consent. Consented participants will be randomized to one of the two study conditions. Based on predictors of smoking behaviors that emerged in our prior work,^{21,23} randomization will be stratified by gender and education level within each clinic. An online random plan generator (<http://www.randomization.com>) will be used to create an allocation schedule. The schedule will be fully documented with the reference citation of the pseudo-random number generator, the seed used to start the generation process, the number of study conditions (2), the allocation ratio (1:1), and a copy of the assignment list.

3.C.4.e. Interventions. All subjects will be offered a 3-month supply of NRT at the enrollment visit. Subjects will be provided an actual supply of nicotine patches or a prescription which can be filled on site (for subjects with insurance coverage). We will encourage study-provided patch use only during the trial.

[Control Condition: American Heart Association Getting Healthy web-program

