Outcome expectations	
 - Improvement in respiratory status - Monetary savings - Urges/cravings for cigs - Weight gain - Enhanced health/longevity 	
 - Possible worsening of depression/anxiety - Weight gain (desirable outcome for many PLWH) 	
 - Perceived Risks and Benefits Questionnaire
Short term			
 - CES-D
Long term		
 - Better long-term CD4+, VL, and survival 	
 - State-Trait Anxiety Scale

Tobacco Use (Aim 1 measures): Self-reported 7-day ppa will be measured at each follow-up and biochemically verified by exhaled carbon monoxide (ECO) at each study visit. Staff will be trained in the use, maintenance, and calibration of the Bedfont piCO+ Smokerlyzer. An ECO measurement of <10 ppm will be considered abstinent and of ≥10 ppm non-abstinent.²³ Discordant self-report and ECO data because of marijuana effects on ECO will be clarified with saliva cotinine strips.¹²⁹ Secondary outcomes include standardized items from the CDC Question Inventory on Tobacco (CDC-QIT)⁹¹ including number of quit attempts, continuous abstinence, and 30-day ppa. Daily cigarette and other tobacco consumption and age at initiation will be assessed. Nicotine addiction will be measured with the Fagerström Tolerance Questionnaire,¹³⁰ and the Contemplation Ladder will measure readiness to quit.¹³¹

Proposed Mediators (Aim 2 measures): Perceived social support will be measured with the Multidimensional Scale of Perceived Social Support to assess perceived general support arising from family, friends, and significant others.^{80,132,133} Smoking-specific social support will be measured with an adapted version of the Partner Interaction Questionnaire.¹⁹ The UCLA Loneliness Scale⁸³ will measure subjective feelings of loneliness or social isolation. [name] Social Support Scale for Smokers (OS4)¹³⁴ – will be adapted to assess dimensions of perceived support from the PSFW+ online community.

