[[In order to calculate the incremental cost per quit, we will compile the costs of website hosting and maintenance, payments to the community administrator and seed users, staff support required to make reminder phone calls, and receipts for nicotine patches. Research costs and development costs for PSFW+ and the portal page for the Control condition will not be included.]]

3.C.6. Data Analysis Plan and Sample Size Calculations

3.C.6.a. Preliminary Analyses. We will calculate descriptive statistics and perform bivariate analyses using t-tests (or nonparametric tests if needed), Chi Square tests (or Fisher's exact tests if needed), and Pearson (or Spearman) correlation coefficients to evaluate relationships among baseline measures (e.g., demographic characteristics), mediating variables (e.g., perceived social support) and outcome measures (7-day ppa). Due to randomization, we expect the two treatment groups to be balanced with respect to the baseline measures. However, baseline measures identified in bivariate analyses as statistically significantly (at the 0.05 level) associated with the outcome measures will be included in the corresponding regression models as covariates to increase statistical power.

[figure not shown]

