3.C.6.b. Specific Aim 1: Outcome Analyses. The primary outcome is 7-day ppa at 6-months.¹⁴⁴ The primary study analyses will adopt an intent-to-treat (ITT) strategy; secondary complete-case, as-treated analyses, and analyses that evaluate the role of treatment intensity (i.e., "dose") will also be conducted. In ITT analyses, the association between treatment group and 7-day ppa at 6-months will be evaluated using a logistic regression model that will have abstinence as the binary outcome, treatment groups as the main predictor, and covariates identified in preliminary bivariate analyses. Subjects who fail to return for the 6-month visit, decline ECO testing, or have discrepant abstinence and ECO results (that cannot be clarified with saliva cotinine strips) will be considered non-abstinent. This is a standard primary outcome when measuring the efficacy of a smoking cessation intervention in a definitive trial.^{21,144} It will be defined as a negative response to the validated question *Have you smoked cigarettes (even a puff) in the last 7 days, including today?*⁹¹ combined with an ECO level <10 ppm (or negative salivary cotinine when applicable).²³ Additional measures of abstinence or tobacco usage reduction will be similarly examined for association with treatment group in secondary analyses.⁹¹ Abstinence data will be collected at 1 and 3 months to assess the correlation between time points. [[A formal cost-effectiveness analysis that includes detailed accounting of effects on health-care utilization over time is beyond the scope of the project. However, we will calculate incremental cost per quit using our abstinence data and the economic metrics listed in 3.C.5. This is a standard cost-effectiveness metric for tobacco treatments,¹⁴⁵ and it will be calculated with bootstrap 95% confidence intervals to provide a starting point for discussions about the cost-economics of tobacco treatment in this population. This outcome is bound to overestimate the ultimate cost of a widely-disseminated intervention, because web-based programs of this sort are scalable at low expense.]]

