Randomization: Following referral from primary care providers, research staff will conduct eligibility screening and informed consent. Once consented, the participant will be randomized to one of the two study conditions. Based on strong predictors of smoking behaviors that emerged in our prior work, randomization will be stratified by gender and education level within each clinic. An online random plan generator (<http://www.randomization.com>) will be used to create an allocation schedule. The schedule will be fully documented with the reference citation of the pseudo-random number generator, the seed used to start the generation process, the number of study conditions (2), the allocation ratio (1:1), and a copy of the assignment list.

Collaborating Sites: [name] (MPI) at Westat will oversee the conduct of the study at Georgetown which is in close proximity to her worksite and with which she maintains an ongoing affiliation. The Georgetown site will recruit participants from the MGUH HIV Clinical Program. [name] will be responsible for recruitment and follow-up at this site, and [name] will oversee the overall conduct of the study at Georgetown. Montefiore Medical Center (MMC) will recruit patients from the MMC Infectious Diseases (ID) Clinic in the Bronx, NY. [name] from MMC will serve as MPI and provide expertise in HIV care and tobacco treatment. [name] and her software development team at the American Legacy Foundation will be responsible for delivering the PSFW+ intervention. They will be responsible for administering the online community and for developing and monitoring the automated tracking metrics on website utilization.

Sources of Materials

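### The primary Aim 1 model takes its covariates from a p<0.05 screen on the trial's own outcome and does not fix the stratification factors in the model (minor)

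*Combined protocol and SAP*

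**What the plan says.** Section 3.C.6.a (Preliminary Analyses) tests baseline measures against the outcome measures in this trial and states that "baseline measures identified in bivariate analyses as statistically significantly (at the 0.05 level) associated with the outcome measures will be included" as covariates in the corresponding regression models. The stated reason is power. Demographic characteristics are given only as an example of the baseline measures; there is no closed candidate list.

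Section 3.C.6.b (Specific Aim 1) builds the primary intention-to-treat logistic model with "treatment groups as the main predictor, and covariates identified in preliminary bivariate analyses". No covariate is named.

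Section 3.C.4.d states that "randomization will be stratified by gender and education level within each clinic". Section 5.A repeats this and gives the reason: "Based on strong predictors of smoking behaviors that emerged in our prior work". Neither section, nor any part of 3.C.6, says that these three factors will be in the model.

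Two other passages promise adjustment for variables that arise after randomisation. Section 3.C.3 would control for use of the control site's smoking module, and section 3.C.7 would adjust for contamination. Neither says whether the primary model is meant.

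**The concern.** A logistic odds ratio is conditional on the covariates in the model. Adding a prognostic covariate moves the target value even when the arms are perfectly balanced. If the covariates are chosen by their p-values against abstinence in the same trial, the quantity that Aim 1 estimates depends on the outcome data. Two analysts could follow the plan faithfully, draw the candidate list differently, and report different primary odds ratios.

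The factors most clearly known in advance are left to this screen. Gender and education were chosen for stratification because earlier work identified them as predictors, yet each must earn its place again at the 0.05 level with few events. At stake is a primary model that can be written down before outcomes are seen.

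**Working it through.** **Inputs.** From section 3.C.6.e: abstinence 15.4% against 7.5%, alpha 0.05, power 0.80, 254 per arm needed, 275 per arm randomised. From 3.C.4.d: 1:1 allocation stratified by clinic, gender and education. The documents give no odds ratios for baseline factors, so those below are assumptions.

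**1. The plan's own figure.** Two-sided, pooled variance, no continuity correction, mean rate 0.1145:

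n = [1.960·√(2·0.1145·0.8855) + 0.842·√(0.154·0.846 + 0.075·0.925)]² / 0.079² = 253.8, so 254 per arm.

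This reproduces. It is an unadjusted comparison, so the covariate rule does not alter it. The planned rates imply an unadjusted odds ratio of (0.154/0.846)/(0.075/0.925) = 2.25.

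**2. Events available to the screen.** Planned effect: 275 × (0.154 + 0.075) = 63.0 quitters. No effect, both arms at 7.5%: 550 × 0.075 = 41.3.

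**3. Chance that one stratification factor is selected.** Take two equal levels and an overall rate of 0.1145. The standard error of the difference between levels is √(0.1145 × 0.8855 × 4/550) = 0.0272.

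| Assumed OR | Rates in the two levels | Expected z | P(p<0.05) |
|---|---|---|---|
| 1.5 | 9.4%, 13.5% | 0.0407/0.0272 = 1.50 | 32% |
| 2.0 | 8.0%, 14.9% | 0.0684/0.0272 = 2.52 | 71% |

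Simulation of the stratified trial (550 subjects, 3,000 trials in each of 18 scenarios) gave 26–32% at OR 1.5 and 60–70% at OR 2.0 for gender or education. Both entered in 7–10% and 37–49% respectively. A clinic factor with no effect entered in 4–6%.

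A separate simulation (log odds ratios 0.4, 0.4 and 0.3 for the three factors; 5,000 trials per scenario) kept on average 0.54 to 0.75 of the three. It selected 2.8 to 4.2 covariates in all.

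**4. Null measures entering by chance.** Counting the measures in section 3.C.5 gives about 24 candidates besides the strata, or 17 if those labelled mediators are left out. The count is mine because the list is open. If all are null and independent:

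- 24 candidates: 24 × 0.05 = 1.20 expected entries; 1 − 0.95²⁴ = 71% chance of at least one.
- 17 candidates: 17 × 0.05 = 0.85; 1 − 0.95¹⁷ = 58%.

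These percentages assume independence. With an assumed common correlation of 0.3 among 24 candidates, 71% falls to 60%; with 0.5, to 46%. The expected count stays at 1.2.

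**5. Effect on the estimate.** In the separate simulation at the planned effect, the mean log odds ratios were 0.821 unadjusted, 0.858 screened and 0.871 with a fixed list, that is odds ratios of 2.27, 2.36 and 2.39. With stronger covariates they were 2.27, 2.49 and 2.51. In a third simulation with correlated candidates and strata OR 1.5, the screened odds ratio lay between about 6% below and 9% above the fixed-list value in 95% of trials.

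**6. Effect on error rates.** The first simulation, pooled over 54,000 trials per column:

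| Model | Type I error | Power |
|---|---|---|
| Unadjusted | 4.39% | 83.51% |
| Screened | 4.78% | 84.74% |
| Strata only | 4.63% | 84.14% |
| Strata plus two named covariates | 4.76% | 84.89% |

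The separate simulation gave power of 84.0%, 83.5% and 86.0% screened against 84.9%, 84.8% and 86.6% fixed. Type I error was 4.7–4.9% screened and 4.6–5.2% fixed. The third gave 87.0% against 87.4% for power and 4.8% against 5.0% for type I error.

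Adding the strata to the screened model changed the p<0.05 result in 0.2–1.1% of trials, with a median odds-ratio ratio of 0.994–0.999.

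**The case against.** The strongest reply is that nothing measurable is harmed. The plan fixes a threshold and restricts the screen to baseline measures, so it is a rule and not free choice. Its stated purpose is met: power rises from 83.5% unadjusted to 84.7%. Error rates are sound. A fixed list with the strata alone has slightly lower power than the screen (84.1% against 84.7%), so equal or better power depends on the named covariates being prognostic. All of this stands, and it is why the point is minor. It does not answer the open candidate list, or the fact that the estimand is settled by the outcome data.

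A second reply is that there are too few events for a fixed model. Arm, clinic, gender, two-level education and two covariates make 6 terms: 63/6 = 10.5 quitters per term at the planned effect, but 41.25/6 = 6.9 under no effect. With three education levels (the documents do not state the number) the figures are 9.0 and 5.9. The separate simulation fitted a 7-term fixed model under no effect, 5.9 quitters per term, and type I error was 4.6–5.2%. The objection does not hold at this size.

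A third reply concerns loneliness. A reader might infer that the plan would wrongly discard a proven predictor. The evidence is mixed. Section 3.C.1.c reports that "Higher loneliness score was an independent predictor of treatment failure" in the group-therapy pilot. In section 3.C.1.f, "Post-hoc analyses were performed on a combined sample (N=272) from the two R21 (PSF & PSFW) trials listed above", and there "Those who were abstinent at 3 months had lower loneliness scores at baseline than those still smoking" with P=0.09. Nor do the documents bar it from the screen: 3.C.6.a screens baseline measures, and loneliness was measured at baseline in the pilots. It is a reasonable candidate for naming, and no more than that.

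**Conclusion.** The point holds as a minor one. The primary model is filled by a significance screen on the trial's own outcome, from an open list, and the three stratification factors are not fixed in it. At an assumed odds ratio of 1.5, gender and education would each be included in about 30% of trials. What is lost is a primary conditional odds ratio that is known in advance.

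Two stronger conclusions are tempting and not supported. One is that the screen inflates type I error or leaves the trial underpowered. Type I error stayed near 5% throughout, and the power difference from a fixed list with named covariates was at most about 1 point. The other is that writing a fixed list now would restore pre-specification. The background to the amendment dated 10-4-21 says that the parent study closed in 2020 and reported 6-month efficacy, so outcomes have probably been seen.

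The percentages rest on assumed covariate effects, two levels per factor and my count of candidates. The textual finding does not.

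**What to change.** Define the primary Aim 1 model as arm, clinic, gender and education, at the levels used in randomisation. Add at most one or two baseline covariates, named from the documents and not from the trial's results. Baseline nicotine dependence and baseline loneliness are examples, the latter with its mixed evidence acknowledged. Use only the baseline value of loneliness, because Aim 2 takes its mediators at 3 months.

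Keep the bivariate screen as descriptive or as a sensitivity analysis. State that post-randomisation variables, such as smoking-module use (3.C.3) and contamination (3.C.7), stay out of the primary intention-to-treat model. Report the unadjusted odds ratio and risk difference alongside.

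If the analysis has not been run, the cost is wording only. If it has, report the strata-adjusted and unadjusted results as labelled additional analyses. That is one re-run on existing data, with no new data or participants, and it should not be presented as pre-specified.

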Missing data. We expect less than 10% missing data at any time. Under an intention-to-treat approach, participants who had been considered non-smokers up to the point of losing contact will be considered relapsers at future data points. Multiple imputation methods¹⁴⁶ will be used to deal with missing data, assuming a missing at random (MAR) mechanism; we will generate 10 multiple imputed datasets, analyze each dataset separately, and then combine the results across the 10 datasets using Rubin's method.

3.C.6.c. Specific Aim 2: Mediator Analyses. Aim 2 hypothesizes that greater social support mediates the intervention-cessation relationship. Figure 3 depicts our mediational model:

X represents treatment group, **Z** represents the hypothesized mediator (e.g., perceived social support), **Y** represents outcome (7-day ppa), **a** is the regression path between treatment group and mediator, **b** is the regression path between mediator and outcome, and **c'** is the regression path between treatment group and outcome controlling for the effect of the mediator. The 3-month assessment will be used for mediator **Z** and the 6-month measure of 7-day ppa will be used as the primary binary outcome **Y**. To increase statistical power of our mediation analysis we will use the product of coefficients method.¹⁴⁷ We will estimate the coefficient **a** by fitting a linear regression model with the putative mediator as the continuous outcome, treatment arm as the main predictor, and covariates identified in bivariate analyses as being associated with social support. We will estimate the coefficient **b** by using a logistic regression model with abstinence as the binary outcome, **Z** as the main predictor, and covariates identified in bivariate analyses as being associated with abstinence. We will then calculate the mediated effect as the corresponding product of these coefficients with standard error and 95% confidence interval estimated according to MacKinnon.¹⁴⁸ Since the sampling distribution of this product shows considerable skewness and kurtosis, interval estimation will be based upon bias-corrected and accelerated (BCA) bootstrap confidence intervals.¹⁴⁹ Potential mediators in Figure 1 will be analyzed separately, and additional analyses will be conducted to evaluate interaction effects.

Figure 3. Mediational Analyses

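### Section 3.C.6.e: 9.2% loss from 275 per arm leaves about 250 per arm and 499 in total, not the stated 254 and 508, which imply 7.6% loss

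*Combined protocol and SAP*

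**What the plan says.** **Sample size (3.C.6.e).** For Aim 1 the plan assumes 6-month abstinence of 15.4% with PSFW+ and 7.5% with control, and gives 254 per arm for power 0.8 at alpha 0.05. It projects 9.2% loss to follow-up, which it calls liberal and bases on two earlier trials, and randomises 275 per arm (550 in total). The Aim 2 statement claims at least 80% power for each mediator at an expected N of 508 at 6 months, which is 2 × 254.

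**Primary analysis (3.C.6.b).** The analysis is intention-to-treat. "Subjects who fail to return for the 6-month visit, decline ECO testing, or have discrepant abstinence and ECO results" are counted as non-abstinent; for discrepant results this applies when cotinine strips cannot settle the matter. Everyone randomised therefore has a primary outcome value. The listed secondary analyses are "secondary complete-case, as-treated analyses, and analyses that evaluate the role of treatment intensity".

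**Missing data (3.C.6.b).** Under intention to treat, "participants who had been considered non-smokers up to the point of losing contact will be considered relapsers at future data points". The next sentence says that multiple imputation "will be used to deal with missing data, assuming a missing at random (MAR) mechanism", with 10 datasets combined by Rubin's method. It does not name the variables or analyses covered.

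**The concern.** The sample-size section links four figures: the number needed, the loss, the number randomised and the number expected at 6 months. Any three should reproduce the fourth, and here they do not. The N=508 that does not follow from 9.2% loss is then used in the Aim 2 power statement, so that statement rests on a number the plan's own loss rate does not deliver.

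A second gap sits beside it. The 254 is treated as the number remaining after loss, yet the primary analysis removes nobody: lost subjects stay in as non-abstinent. The plan never states power for that analysis, nor whether 15.4% and 7.5% are rates among all randomised or among those followed.

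At stake is whether the written justification is correct and can be checked. The validity of the trial is not in question.

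**Working it through.** **Inputs.** From 3.C.6.e: p1 = 0.154, p2 = 0.075, alpha 0.05, power 0.80, 254 needed per arm, 9.2% loss, 275 randomised per arm, N=508 for Aim 2. From 3.C.2: 550 in total. The plan does not state whether the test is one- or two-sided. Two-sided is assumed because it reproduces 254; one-sided gives 200.

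**1. Reproduce 254.** Pooled two-proportion formula without continuity correction:

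n = [1.960·√(2·p̄(1−p̄)) + 0.842·√(p1(1−p1) + p2(1−p2))]² / (p1−p2)², with p̄ = 0.1145.

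- 2·p̄(1−p̄) = 0.2028 (square root 0.4503), and 1.960 × 0.4503 = 0.8826
- p1(1−p1) + p2(1−p2) = 0.1303 + 0.0694 = 0.1997 (square root 0.4468), and 0.842 × 0.4468 = 0.3761
- n = (1.2587)² / 0.079² = 1.5842 / 0.006241 = 253.8, so 254. The plan's figure is right.

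**2. Apply the stated loss.**

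- 275 × (1 − 0.092) = 249.7 per arm, against 254
- 550 × (1 − 0.092) = 499.4 in total, against 508 (8.6 fewer, 1.7%)

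**3. Try the inflation in the other direction.**

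- 254 / 0.908 = 279.7
- 254 × 1.092 = 277.4

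Neither gives 275.

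**4. Find the loss that fits.** 1 − 254/275 = 21/275 = 7.6%, and 1 − 508/550 = 42/550 = 7.6%. Expressing the extra 21 as a share of 254 gives 8.3%, which is not 9.2% either.

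**5. Power for Aim 1.** Power = Φ{[0.079 − 1.960·√(0.2028/n)] / √(0.1997/n)}:

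| n per arm | Rates | Power |
|---|---|---|
| 250 | 15.4% / 7.5% | 0.794 |
| 254 | 15.4% / 7.5% | 0.800 |
| 275 | 15.4% / 7.5% | 0.831 |

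For the primary analysis all 275 are kept. If the planning rates hold for everyone randomised, the last row applies. If they hold only among those followed and 9.2% are lost and counted as smoking, the rates become 0.154 × 0.908 = 13.98% and 0.075 × 0.908 = 6.81%. The same formula with those rates gives 0.789 at 275 per arm.

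**6. Power for Aim 2.** The plan takes this from a cited source and does not show the calculation, so it is not reworked here. The input that changes is N, from 508 to 499, if 9.2% is kept.

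**The case against.** **The slip has no practical effect.** This largely stands. It is about 4 subjects per arm and 0.6 points of power. Section 3.C.7 reports 4.8% aggregate loss in three tobacco trials at the MMC clinic, and 550 × 0.952 = 523.6, above 508. The two trials cited for the 9.2% lost about 4% of 147 (5.9) and 3% of 138 (4.1), roughly 10/285 = 3.5%. So N=508 may well be reached. It still does not follow from the loss the plan states.

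**The planning rates look like all-randomised rates, which would put power at 0.83.** This has force. The web pilot in 3.C.1.e enrolled 138 and reported 10.1% against 4.3%. Assuming equal arms of 69, 7/69 = 10.1% and 3/69 = 4.3%, which fits all 138 subjects. The documents do not give the arm sizes, however, and 3.C.6.e does not say which basis applies to 15.4% and 7.5%.

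**A reader might infer that the trial is underpowered and needs 280 per arm.** The documents do not support this. The primary analysis does not discard lost subjects, and its power is between about 0.79 and 0.83.

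**A reader might infer that multiple imputation conflicts with the primary rule.** That is not shown. Once missing values are set to non-abstinent, no 6-month primary value remains to impute. Imputation still has natural targets:

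- baseline covariates, since "baseline measures identified in bivariate analyses as statistically significantly (at the 0.05 level) associated with the outcome measures will be included" in the models;
- mediators, since "The 3-month assessment will be used for mediator" Z;
- tobacco-reduction measures.

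Secondary abstinence measures, "including number of quit attempts, continuous abstinence, and 30-day ppa", are less explicit. But "Additional measures of abstinence or tobacco usage reduction will be similarly examined for association with treatment group in secondary analyses", and the relapse rule is not confined to month 6, so the text points to missing counted as smoking.

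**A reader might infer that the missing-data rule could swing the result if loss differed by arm.** The documents project no such difference, so any figure for it would rest on an invented split.

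**Conclusion.** Section 3.C.6.e contradicts itself. With 275 per arm, 9.2% loss gives about 250 per arm and 499 in total; 254 and 508 require 7.6% loss. The N=508 in the Aim 2 statement shares the inconsistency. The 254 itself is correct.

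The size is minor: under one point of power for a completer comparison. Whether the planning rates describe all randomised or only those followed matters more, at about 4 points (0.831 against 0.789), and the plan should say which. These figures assume a two-sided test, no covariate adjustment and, for 0.789, equal loss in both arms. The unstated scope of multiple imputation is a matter of wording and leaves the primary analysis intact.

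**What to change.** In 3.C.6.e, choose one consistent set of figures:

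- keep 9.2% loss, restate about 250 per arm and N=499, give completer power as about 0.79, and recompute the Aim 2 power at N=499; or
- restate the projected loss as 7.6% and keep 254 per arm and N=508.

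In either case, add one sentence giving power for the primary intention-to-treat analysis with all 275 per arm and missing counted as non-abstinent. Say whether 15.4% and 7.5% are all-randomised rates (about 0.83) or rates among those followed (about 0.79 at 9.2% loss; about 0.80 at 7.6%).

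Optionally, add a sentence to the missing-data paragraph naming what multiple imputation covers and confirming that it does not replace the non-abstinent rule for the primary outcome.

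The cost is a corrected figure or two, a sentence or two and, under the first option, one recalculation for Aim 2. No extra participants, visits or data are needed.
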